8.2 Randomisation Procedures

Following participant consent, and confirmation of eligibility at the screening visit (see section 8.1 for pre-treatment assessments), the participant will be allocated a participant trial number and the randomisation procedure described below will be carried out. An independent statistician will generate the randomisation list which will be uploaded to REDCap (an online randomisation database) for online concealed allocation. Participant randomisation will then be undertaken centrally by the coordinating team using REDCap. Participants will be randomised to either the Hearing Intervention or Healthy Ageing Intervention by computer programme on a 1:1 ratio. The randomisation list and the Trial Subject Log will be kept by the trial manager. The audiologist will receive by secure communication the participant's allocation to the Hearing or Healthy Ageing Intervention.

Participants are considered to be enrolled into the trial following: consent, pre-treatment assessments (see section 8.1), confirmation of eligibility, completion of the randomisation process, allocation of

the participant trial number and intervention by the central coordinating team.

The RHI sub-study (during COVID-19) will not be randomised. All participants will be allocated to the RHI.

8.3 Intervention procedures

Rationale for intervention delivered in home visits

The Hearing Intervention is a home-based intervention. The intervention will be delivered at participants' homes, unless the participant prefers otherwise (in which case it will be delivered at UCL premises), by a research audiologist in combination with a graduate psychologist research assistant. The intervention will be manualised to facilitate standardisation and scalability, but will also be individualised according to the individual's needs and circumstances. If available, a communication partner will also participate in the intervention. Our previous research has shown that the standard audiological pathway that relies on patients proactively attending appointments in NHS clinics is likely to result in many participants not receiving hearing aids or not using them. Attending clinic appointments is a challenge and barrier for care in this population, as people often forget their medical appointment and misplace reminders. This is consistent with the experience of the researchers in the trial who are also clinicians working with people with cognitive impairment and dementia ([name], [name]), where our Islington Memory service, which, unusually, is almost entirely based on home visits, has achieved near-complete detection of dementia, whilst in many areas dementia diagnosis only reaches 50% of people with the condition. Home visits will also facilitate engagement and reduce anxiety in participants, as well as helping our researchers understand the patient environment and routine, which will be essential to personalise the audiological objectives to each individual participant and lifestyle, as well as helping to integrate hearing aid use into the participant's daily routine.

Overview of the Hearing Intervention and timing of intervention visits

Bilateral, behind the ear (BTE) or receiver in the canal (RIC) hearing aids will be fitted, depending on the participants' characteristics as determined by audiological assessment at the screening visit. The hearing aids will have wireless data logging capabilities, allowing objective recording of adherence, independent of the participant recall. Hearing aids with rechargeable batteries will be used, whenever possible, to minimise and facilitate maintenance. For participants in the Healthy Ageing arm that obtain hearing aids through the NHS or the private sector, we will request permission to download usage data from their devices. We anticipate that in most cases, and particularly for NHS provided hearing aids, we will be able to obtain usage data through data logging. We will collect any failures to obtain data logging from hearing aids as secondary outcomes for the trial.

These hearing aid devices will have fitting and verification procedures that can be conducted at the participant's home. The setting up of the hearing aids will be personalised to maximise audibility and incorporate appropriate noise reduction. Participants will complete a calendar to record their daily use, which will act as a reminder for use. Hearing aids placement, operation and maintenance will be explained, with advice adapted to the person's routine.

We will work with the participant and any family carers to understand the participant's routine and identify practical ways to integrate hearing aid use into their habits by finding specific times of putting on and taking out the hearing aids. A specific spot in the home will be identified at this visit for hearing

aids to be stored when unused in a specific box provided by the trial, which will also contain the usage calendar, literature on how to troubleshoot any practical difficulties, and a hotline (phone and email) to the researchers if that fails. Personalised information on how the hearing aid fits into the participant's routine, in the form of a written schedule of activities for a typical day, will be left with the participant on the cover of the box containing the hearing aids, so that it acts as a reminder of use.

A personalised report on hearing aid use based on data logging will be provided using a traffic light system with red for low use, and additional support will be provided at the visit if needed.

The intervention sessions are anticipated to occur according to the following schedule:

 - Demonstration and training on using hearing aids
 - Videos on “adapting to wearing hearing aids”
 - Discussion on realistic expectations: expected benefits and typical initial difficulties (own voice quality, whistling, loud noises); adaptation to hearing aids as a learning process
 - Review of integration in daily routine and use of reminders
 - Provide calendar to record hearing aid use
 - Adverse events questionnaire

Healthy Ageing Intervention – Session B (V3)

- Visit will be delivered by RA. The visit will focus on
 - Lesson: Eat a healthy diet
 - If applicable: self-report on hearing aid use & data logging (with support from the Audiologist if required)
 - Adverse events questionnaire

Hearing Intervention – Session C (V4)

- Visit will be delivered by RA or research audiologist and will include the communication partner, if applicable. It will focus on
 - HA usage estimate
 - Data logging
 - Calendar check & self-report
 - Reviewing integration of hearing aid use in routine
 - Hearing aids benefits (against COSI objectives)
 - Hearing aids problems: placement and typical initial difficulties
 - Practical aspects: batteries, cleaning, maintenance
 - Questionnaire on need for help for hearing aid use
 - Review and reinforce hearing aid orientation and training as needed
 - Videos on “adapting to wearing hearing aids”
 - Realistic expectations
 - Communication strategies that complement hearing aid use and strategies for communication in noisy environment
 - Task 1: as selected by participant from their personalised COSI goals. Feedback on HA use and communication strategies.
 - Adverse events questionnaire

Healthy Ageing Intervention – Session C (V4)

- Visit will be delivered by RA. The visit will focus on
 - Lesson: Be physically active
 - If applicable: self-report on hearing aid use & data logging (with support from the Audiologist if required) and questionnaire on need for help for hearing aid use.
 - Adverse events questionnaire

Hearing Intervention – Session D (V5)

- Visit will be delivered by the research audiologist and will include the communication partner, if applicable. It will focus on
 - HA usage estimate
 - Data logging
 - Calendar check & self-report
 - Reviewing integration of hearing aid use in routine
 - Fine tuning and optimisation of HA fitting including programming adjustments (if required)
 - Review of any ongoing specific difficulties
 - Electroacoustic analysis (if required)
 - Real Ear Measurements
 - Questionnaire on need for help for hearing aid use
 - Review of goal-setting (COSI), any progress made, and barriers to progress
 - Reinforcing and review of communication strategies introduced in Session C
 - Review and reinforce hearing aid orientation and training as needed
 - Adverse events questionnaire
 - Participant rating of the acceptability of the Hearing Intervention using a 5-point Likert scale.

Healthy Ageing Intervention – Session D (V5)

- Visit will be delivered by RA. The visit will focus on
 - Lesson: Maintain healthy bones, joints and muscles
 - If applicable: self-report on hearing aid use & data logging (with support from the Audiologist if required) and questionnaire on need for help for hearing aid use.
 - Adverse events questionnaire
 - For those participants who have not received/sought medical advice for their hearing loss: At the end of session D the RA will remind the participant (and their communication partner where applicable) that their hearing test suggested they have hearing loss and the participant will be advised to follow this up with their GP.
 - Participant rating of the acceptability of the Healthy Ageing Intervention using a 5-point Likert scale.

Additional contact and irregular visits

In addition to the above visits, participants will be contacted through optional SMS to remind them to use the hearing aids and reinforce calendar completion (in the Hearing Intervention Arm). Within the first week after hearing aid fitting, and between visits afterwards, participants will be contacted via

telephone if feasible, or through alternatives (family, the post or visits) to make sure that the hearing aids are working. After the intervention visits are finished we will also proactively contact the participant monthly afterwards through telephone if feasible, or through alternatives.

Additional contact (email, telephone or visits) with the RA or the research audiologist may be scheduled to provide troubleshooting of practical problems or additional training, with the agreement of the trial manager or CI. This can be motivated by participant or by the investigator. The number, modality, goal and duration of contact will be logged and used as a secondary trial outcome to see if the intervention is sufficient as planned.

Intervention in the RHI sub-study (during COVID-19)

The RHI will replicate the Hearing Intervention during COVID-19. The hearing aids will have been programmed by the research audiologist based on the audiogram obtained at the TACT screening visit.

Participants will be provided with these hearing aids and an adapted toolkit, factsheet, calendar sheets and DVD of video clips on hearing aids operation and management (Figure 3). Hearing aid use will be remotely supported by the study team, including programmed contact and, if required, troubleshooting by the audiologist. The following will be planned contacts of the RHI:

Contact 1: Pre-intervention – consent and baseline assessments

Contact 2: Hearing aids are posted to participant, along with:

- Spare domes, spare wax filters and a retention hook
- A4 Factsheet (includes first steps to take on receiving the package)
- Participant toolkit (includes hearing aid diary)
- DVD of video clips
- Calendar sheets (to use as a reminder for inserting/removing the hearing aids)
- Note which includes the date to expect the first call from the audiologist, and contact details for the team (to use for any troubleshooting issues)

Contact 3: Audiologist calls 3 days (+/- 2 days) after hearing aids arrive (expected duration 30-60 minutes total).

- Have they have received HA and tried them?
- Explore motivation to wear HA
- Communication strategies
- Troubleshooting of any issues
- Self-report hearing aids use
- Adverse events questionnaire

Contact 4: RA/Audiologist calls participant 1 week (+/- 1 week) after contact 3 (expected duration 30-60 minutes total).

- Troubleshooting of any issues
- Self-report hearing aids use

- Explore motivation to wear HA
- Adverse events questionnaire

At the end of the RHI there will be an outcome collection contact (contact 5) described in the next section.

Remote contact will also be used by the researchers to remind participants to wear their hearing aids and promote hearing aid use, and to troubleshoot any emerging difficulties. Between contact 3 and contact 5, participants will receive weekly texts with the following: "Are you experiencing any problems with your hearing aids? If so, please contact the team on this *mobile number". Ad-hoc remote contact and postage of hearing aids (for adjustment/repair, with postage paid by the study) between the participant and the audiologist can also be scheduled if required at the request of the participant and at the discretion of the audiologist.

Any of the study contacts can be split over two or several telephone calls, if requested by the participant or at the researcher's discretion.

8.4 Subsequent assessments and procedures

Assessment of adherence

Adherence includes adherence to both hearing aids and protocol trial procedures. Adherence to hearing aid use will be monitored by data-logging and participant self-report and calendar. However, adherence to hearing aids is an outcome of the trial and it would therefore be inappropriate to set a minimal compliance target to remain in the trial. Noncompliance to the protocol procedures will be documented by the investigator and reported to the Sponsor as agreed. Participants who do not fully adhere to the intervention will still be followed and assessed as per trial procedures.

Outcome assessment: Follow-up visit at 6 months (V6)

Purpose: to gather outcome measures of primary and secondary outcomes.

When: 6 months post-randomisation (with a tolerance of +/- 4 weeks)

This visit will be conducted by the RA who will first collect information about hearing aid usage:

- HA usage estimate
 - Data logging
 - Calendar check & self-report

The RA will also try to collect data logging information for Healthy Ageing participants who received treatment as usual for audiological care and were provided with hearing aids through either the NHS or the private sector.

The following trial procedures will be conducted at this visit by the RA, with participant:

- administer neurocognitive battery
 - Speech audibility procedure (ensuring speech understanding for tests)
 - Delayed word recall test (DWRT): encoding [23]
 - Addenbrooke Cognitive Examination (ACE-III) [22]
 - Trail Making Test (TMT) Part A and B [25]
 - Delayed word recall test (DWRT): recall

- Self-reported hearing disability - Hearing Handicap Inventory for the Elderly – Screening version (HHIE-S)
- Quality of life questionnaires
 - o Short Form 36
 - o EQ-5D
- Four-items (A,F,G,H) of Lawton – Brody Instrumental Activities Of Daily Living Scale
- Question: any falls over the past 6 months.
- Social function scale SF-DEM – patient rated version
- UCLA Loneliness Scale
- Grip strength
- Downloading data from accelerometer
- Adverse events questionnaire
- Client Oriented Scale of Improvement (COSI)
- Questionnaire on need for help for hearing aid use

If a communication partner is present, the following procedures will be conducted with the communication partner:

- Quality of their communication with the participant and HL impact: The Hearing Impairment Impact–Significant Other Profile
- Health-related quality of life of communication partner: SF36 and EQ-5D
- Hospital anxiety and depression HADS, validated in caregiver population
- Proxy information on participant:
 - o Carer-rated version of the SF-DEM .
 - o Lawton – Brody Instrumental Activities Of Daily Living Scale (I.A.D.L.)

The accelerometer will be recovered by a research assistant one week after outcome assessment visit.

At the end of the trial the participants will be able to keep the hearing aids, which will be covered by the standard guarantees of the manufacturer. If, after the trial, the participants require further audiological advice or care they will be advised to consult their GP to seek a referral to NHS audiological services.

Outcome assessment: Early Discontinuation Visit

In case of Early Discontinuation, we will attempt to conduct a visit with the same procedures as the Follow-up visit at 6 months as far as possible.

Outcome assessment for the RHI sub-study: Contact 5

At the end of the RHI there will be an outcome collection contact (contact 5). Outcome collection will be done at 4 weeks (+/-2 weeks) after receiving the hearing aids (expected duration 45-60 minutes total). These will include the same assessment tools administered at the RHI sub-study baseline assessment (a simplified version of the TACT assessment battery), namely:

- Mood: Geriatric depression scale (GDS) [28]
- Cognition: Addenbrooke Cognitive Examination (ACE-III) [22]; these will include only those items that can be obtained by remote assessment

- Hearing: Review of personalised goal-setting for the RHI, using the Client Oriented Scale of Improvement (COSI; developed by the National Acoustic Laboratories of Australia); discussion of any progress made, and barriers to progress.

We will also collect at this contact:

- Participant rating of the acceptability of the RHI using a 5-point Likert scale.
- Adverse events questionnaire
- Collection of information about hearing aid use by self-report & calendar check.

8.5 Samples (if applicable) N/A

8.5.1 Laboratory assessments N/A

8.5.2 Translational research samples (if applicable) N/A

8.5.3 Sample storage and transfer N/A

8.6 Discontinuation/withdrawal of participants

Given that hearing aids are generally considered to be a safe treatment, we do not envisage safety reasons that might result in premature termination from the trial, or that put a complete stop to the trial. Subjects will be withdrawn from the trial if they request it for any reason. Subjects who misplace their hearing aids will not be withdrawn from the trial, instead they will be offered a replacement (up to two times only at the discretion of the audiologist). If they misplace them a third time then they will be offered to remain in the trial until end of their follow-up, but they will not receive any further hearing aids.

The decision to withdraw a participant from treatment will be recorded in the CRF and medical notes. If a participant explicitly states they do not wish to contribute further data to the trial their decision must be respected and recorded in the CRF and medical notes.

8.7 Definition of End of Trial

The expected duration of the trial is 24 months from recruitment of the first participant.

The end of the trial is the date of the last visit of the last participant.

9 Recording and reporting of adverse events

9.1 Definitions

Term	Definition
-------------	-------------------

Adverse Event (AE)	Any untoward medical occurrence in a patient or trial participant, which does not necessarily have a causal relationship with the intervention involved.
Serious Adverse Event (SAE).	Any adverse event that: 
 • results in death, • is life-threatening*, • requires hospitalisation or prolongation of existing hospitalisation**, • results in persistent or significant disability or incapacity, or • consists of a congenital anomaly or birth defect.

* A life- threatening event, this refers to an event in which the participant was at risk of death at the time of the event; it does not refer to an event which hypothetically might have caused death if it were more severe.
 
** Hospitalisation is defined as an in-patient admission, regardless of length of stay. Hospitalisation for pre-existing conditions, including elective procedures do not constitute an SAE.
	

9.2 Assessments of Adverse Events

Each adverse event will be assessed for severity, causality, seriousness and expectedness as described below.

9.2.1 Severity

The generic categories below are given for use as a guide. You may have a more specific scale that you want to use related to the disease (e.g. CTCAE criteria), amend as required.

Category	Definition
Mild	The adverse event does not interfere with the participant's daily routine, and does not require further intervention; it causes slight discomfort
Moderate	The adverse event interferes with some aspects of the participant's routine, or requires further intervention, but is not damaging to health; it causes moderate discomfort

Severe	The adverse event results in alteration, discomfort or disability which is clearly damaging to health
--------	---

9.2.2 Causality

The assessment of relationship of adverse events to the intervention is a clinical decision based on all available information at the time of the completion of the Case Report Form (CRF).

If a differentiated causality assessment which includes other factors in the trial is deemed appropriate, please add/amend the following wording to specify:

It is of particular importance in this trial to capture events related to the procedure (specify e.g. surgery) / product failure / mandatory concomitant medications / device(s) (refer to section 9.17 for reporting requirements). The assessment of relationship of an adverse event to this/these additional safety issue(s) will also be carried out as part of the trial.

The differentiated causality assessments will be captured in the trial specific CRF/AE Log and/or SAE form (amend as required).

The following categories will be used to define the causality of the adverse event:

Category	Definition
Definitely:	There is clear evidence to suggest a causal relationship, and other possible contributing factors can be ruled out.
Probably:	There is evidence to suggest a causal relationship, and the influence of other factors is unlikely
Possibly	There is some evidence to suggest a causal relationship (e.g. the event occurred within a reasonable time after administration of the trial intervention). However, the influence of other factors may have contributed to the event (e.g. the participant's clinical condition, other concomitant events).
Unlikely	There is little evidence to suggest there is a causal relationship (e.g. the event did not occur within a reasonable time after administration of the trial

	intervention). There is another reasonable explanation for the event (e.g. the participant's clinical condition, other concomitant treatments).
Not related	There is no evidence of any causal relationship.
Not Assessable	Unable to assess on information available.

9.2.3 Expectedness

Category	Definition
Expected	An adverse event which is consistent with the information about the intervention listed in the SPC, manual of Operation (amend as appropriate) or clearly defined in this protocol.
Unexpected	An adverse event which is not consistent with the information about the intervention listed in the SPC, manual of Operation (amend as appropriate)* or clearly defined in this protocol.

* This includes listed events that are more frequently reported or more severe than previously reported.

The following events listed below describe expected procedural/disease related AEs: Otitis externa, cerumen impaction or ear foreign body requiring removal by a physician.

9.3 Recording adverse events

Hearing aids are generally considered to have low risk of adverse events. Trial participation and exposure to the hearing aid intervention is therefore expected to have a low risk of adverse events for the participant. At the same time, the age of the participants may naturally lead to numerous deleterious health outcomes unrelated to the trial. We will therefore collect safety information that is relevant to trial participation, interventions, and procedures, as well as any serious AE. A pre-specified set of adverse events and serious adverse events will be collected and evaluated throughout

the conduct of the trial: Otitis externa, cerumen impaction or ear foreign body requiring removal by a physician. This set of AEs, as well as all serious adverse events, will be recorded in the CRF.

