3.1 Assessment and Management of Risk

Adverse effects: Hearing aids are generally considered a safe treatment without clinically significant adverse effects, although safety has been identified as an understudied topic in clinical trials of hearing aid efficacy [12]. The only RCT in people with cognitive impairment and dementia to have reported on adverse effects [13] did not identify any side effects over 6 months in a sample of 48 patients.

Dizziness, nervousness and headaches are considered rare but possible adverse effects, probably linked to poor fitting of the hearing aids. In consumer surveys [14] symptoms of local discomfort have been reported, but no more serious adverse events. Noise-induced hearing loss, due to over-amplification from inappropriate hearing aid fitting is a possible but unverified adverse effect.

These risks will be minimised through strict adherence to best practices recommendations for hearing assessment and hearing aid fitting from the British Society of Audiology. We will also incorporate the upcoming NICE guidelines which are expected to be published in May 2018 [Hearing loss in adults: assessment and management; National Guideline Centre; <https://www.nice.org.uk/guidance/indevelopment/gid-cgwave0833>]. This is the same guidance followed within NHS audiological services. Therefore, we do not expect increased risk of our intervention for participants relative to normal standard practice, when it is considered to be a low risk intervention.

¹ Guidance On The Management Of Clinical Trials During The Covid-19 (Coronavirus) Pandemic (28/04/2020). European Medical Agency [https://ec.europa.eu/health/sites/health/files/files/eudralex/vol-10/guidanceclinicaltrials_covid19_en.pdf].

² A framework for restarting NIHR research activities which have been paused due to COVID-19 (21/05/2020). National Institute for Health Research [<https://www.nihr.ac.uk/documents/restart-framework/24886>]

In our trial we will proactively ask participants about potential side effects, and, if present, they will be reviewed by the research audiologist to identify whether these issues can be remedied by adjusting the hearing aid fitting, or if they require assessment by GP or secondary services.

This trial is categorised as:

- Type A = No higher than the risk of standard medical care

The table below summarises the risks and mitigations of all tests above standard care that are being performed:

Intervention	Potential risk	Risk Management

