11.6.3 Secondary outcome analysis

We will report the number of participants consented, screened, randomised and completing the trial as per trial workflow (Fig. 3).

We will estimate:

- Difference between the Hearing Intervention and the Healthy Intervention arms, in the proportion of participants maintaining hearing aid use, defined as a minimum of 4h a day on average since last trial assessment (when at home and in usual health) as established by data-logging at 6 months (end of trial), based on the hearing aid with the highest average use (as each participant has two hearing aids). Self-reported hearing aid use may also be employed if needed, for instance if no data-logging is available for a participant, as further specified in the Statistical Analysis Plan.
- Percentage of participants rating the interventions (Hearing Intervention and Healthy Ageing Intervention) as acceptable (ratings 3-5 on a 5-point Likert scale) based on Likert scale scores.
- Mean, proportions, differences in means and proportions across treatment arms with corresponding 95% confidence intervals will be calculated as appropriate for the cognitive scales and other trial outcomes, to inform the sample size calculation for a full scale trial.

We will produce appropriate summary estimates and report the following:

- Number of potential participants referred to the study researchers, screening visits scheduled and completed.
- Feasibility of the schedule of assessments, which will include proportion of completed interviews and completion rates of instruments and questionnaires, as well as relevant biometric data.
- Completion rates of the interventions by recording the proportion of participants who completed the intervention, any refused or discontinued visits for the Hearing Intervention and Healthy Ageing Intervention, and any refused or discontinued tests and instruments from the schedule of assessments.
- For the Hearing Intervention, we will record the number of participants with hearing aid fitted within 3 months (target: 80%) and reported side effects.
- Average hearing aid daily use measured as number of hours of use on average over 7 days (when at home and in usual health) as established by data-logging at 6 months (end of trial) for the Hearing Intervention and Healthy Ageing Arms. Self-reported hearing aid use may also be employed if needed, for instance if no data-logging is available for a participant, as further specified in the Statistical Analysis Plan.

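### The adverse-event set that section 9.3 sends to the CRF contains none of the hearing-aid effects named in section 3.1, and the source of the side-effect outcome is not stated

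*Protocol*

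**What the plan says.** Section 9.3 opens broadly: "We will therefore collect safety information that is relevant to trial participation, interventions, and procedures, as well as any serious AE". It then names a pre-specified set, "Otitis externa, cerumen impaction or ear foreign body requiring removal by a physician", and gives the recording rule: "This set of AEs, as well as all serious adverse events, will be recorded in the CRF". Section 9.2.3 lists the same three ear events as the expected adverse events.

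Section 3.1 describes what hearing aids might cause, in three statements:

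- "Dizziness, nervousness and headaches are considered rare but possible adverse effects, probably linked to poor fitting of the hearing aids"
- users surveyed as consumers mentioned local discomfort and nothing graver
- "Noise-induced hearing loss, due to over-amplification from inappropriate hearing aid fitting is a possible but unverified adverse effect"

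The same section says that participants will be asked actively about side effects and that the research audiologist will review any that are present.

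Sections 8.3 and 8.4 schedule an adverse events questionnaire at Sessions A to D in both arms, at the 6-month visit, and at contacts 3, 4 and 5 of the Remote Hearing Intervention (RHI) sub-study. Its items are not shown.

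Side effects are an outcome. For the Hearing Intervention, section 11.6.3 says "we will record the number of participants with hearing aid fitted within 3 months (target: 80%) and reported side effects", and section 11.2 has the same item. Section 11.6.3 ends with a separate reporting line for side effects that names no arm.

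**The concern.** The protocol calls the safety of hearing aids an understudied topic and lists the effects it considers possible. Its one explicit rule on what enters the CRF then names a different set of events. If data entry follows that rule and the side-effect outcome is built from it, non-serious dizziness, headache, nervousness, local discomfort or hearing change could be reported to the team and still not appear in the result.

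Two things make this matter. The Trial Steering Committee is to consider the secondary outcomes when it decides whether to proceed to the main trial (section 11.3). And in the RHI sub-study the aids are programmed from the earlier screening audiogram and posted, with no face-to-face visit. Section 3.1 links dizziness, nervousness and headache to poor fitting, yet section 9.3 sets no wider recording for that sub-study.

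**Working it through.** The protocol states no adverse-event rate or precision figure that depends on the recording rule, so there is nothing to recalculate. The check is a comparison of sections.

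**Step 1. Effects named in 3.1 against the set in 9.3**

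| Effect named in 3.1 | In the 9.3 set? | Stated CRF route |
|---|---|---|
| Dizziness | No | If serious |
| Nervousness | No | If serious |
| Headache | No | If serious |
| Local discomfort | No | If serious |
| Noise-induced hearing loss | No | If serious, for example through the disability criterion in 9.1 |

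The overlap is 0 of 5. Section 9.2.3 does not close the gap, because it repeats the three ear events.

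**Step 2. Is the set meant as a limit?** Section 9.3 does not use the word only, and its opening sentence on collection is broad. But its order points to targeted recording: many unrelated health events are expected at this age, so relevant safety information is collected, so a set is pre-specified, and that set goes to the CRF. A pre-specified set would have little purpose if every non-serious event were recorded anyway. The text supports a narrow reading without stating it outright.

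**Step 3. Do other routes supply a CRF destination?**

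- Active asking (3.1): provides for audiologist review, but names no place of recording.
- Adverse events questionnaire (8.3, 8.4): given in both arms and in the RHI sub-study, but the protocol does not say where non-serious answers outside the set are recorded.
- Source documents (10.2): participant questionnaires are the example given of data that stay out of the CRF. Which data do so is left to a source document list that is not shown.
- Adverse Event log (15): sent to the sponsor each year; its scope is not stated.
- Severity grades (9.2.1): the mild and moderate grades refer to discomfort, which implies that non-serious events are assessed, but does not say where they are entered.

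These routes show an intention to capture side effects. None links a non-serious 3.1 effect to the CRF or names the data source of the outcome.

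**Step 4. Arms.** Section 11.2 and one bullet of 11.6.3 attach side effects to the Hearing Intervention. The closing line of 11.6.3 names no arm, and 11.6.3 also plans differences across arms with 95% confidence intervals for other trial outcomes. The questionnaire is given in both arms. The wording is inconsistent about arm, but control-arm reporting is possible under the plan.

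**The case against.** The strongest reply is that the protocol plainly means to capture side effects. It asks about them, gives a questionnaire at every intervention session and at follow-up, and promises to report them without restricting them to three ear events. The natural source of the outcome is the questionnaire, and data held outside the CRF are not lost to analysis. Targeted recording is also reasoned: the device is low risk, section 3.1 calls dizziness, nervousness and headache rare, and it cites a randomised trial with no side effects in 48 patients. Side effects are not among the four progression estimates in 11.3.

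Much of this stands, and it rules out three stronger readings that a reader might infer:

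- **That side effects will be under-counted.** This would follow only if the outcome were taken solely from the 9.3 set, and no section says so.
- **That every case of the 3.1 effects is left out.** A case that meets the serious adverse event definition is recorded.
- **That the control arm is excluded.** The closing line of 11.6.3 is not limited to an arm, and control participants complete the questionnaire.

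What does not fall is the conflict itself. The only stated CRF rule omits all five effects, and no section says where their non-serious cases go. A statistical analysis plan could name the source of the outcome, but what is entered in the CRF is fixed here, in section 9.3.

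**Conclusion.** The sections are inconsistent and need to be reconciled. The set that 9.3 sends to the CRF covers 0 of the 5 effects named in 3.1, although the protocol asks about side effects and reports them as an outcome. The consequence is a risk of under-counting, conditional on the outcome being drawn from the 9.3 set. Its size cannot be given, because the protocol states no side-effect rate and the questionnaire items are not shown. The conclusion rests on reading the 9.3 rule as written and on the absence of any other stated CRF route for non-serious cases. It does not touch the primary feasibility outcomes. The change is worth making because it is cheap and bears on what reaches the analysis dataset.

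**What to change.** 1. In section 9.3, add the effects named in 3.1 (dizziness, nervousness, headache, local discomfort, and hearing change or other complaints suggesting over-amplification) to the recorded set, for both arms and for the RHI sub-study. Appendix 1 schedules pure-tone audiometry at screening only, so at later visits the hearing item would be a reported change, not a measured threshold shift.
2. State that adverse events questionnaire answers, entered in the CRF or trial database, are the source for the side-effect outcome. Align the source document list in 10.2 with this.
3. Make section 11.2 and the Hearing Intervention bullet in 11.6.3 agree with the arm-neutral line that closes 11.6.3, and report side effects by arm.
4. For the 36 participants randomised before the pandemic, enter the questionnaire answers from source where they were kept.

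The cost is slightly more adverse-event data entry and assessment, and one table by arm. No new visit or instrument is needed, because the questionnaire is already given.
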